Archive blood samples (protein and mRNA biomarkers) ^v		X								X							X			
Blood DNA for genomics ^w		X																		

- a Randomization/baseline Visit is defined as Day 1. Visit windows for subsequent visits are +/- 2 days.
- b All assessments at Visit 2 (Day 1) are to be conducted predose with the exception of the assessment of local tolerability of SC injections.
- c Supplementary calls may be made to supply IMPs kits directly to patient's home.
- d Study treatment to be administered once a week, either at the site level or at home by a nurse.
- e Complete physical examinations will include skin, nasal cavities, eyes, ears, respiratory, cardiovascular, gastrointestinal, neurological, lymphatic and musculoskeletal systems. [REDACTED] Nail beds (periungual areas) should be examined for "splinter lesions" and digital tuft for tuft purpura or ischemia. Gynecological and urogenital examinations will not be done in this study unless for cause.
- f Vital signs, including blood pressure (mmHg), heart rate (beats per minute) and body weight (kg) will be measured at screening, baseline and every subsequent visit. Height (cm) will be measured at screening (Visit 1) only. BMI will be calculated automatically at all visits.

- g* Hematology: Hemoglobin, hematocrit, red blood cell count, erythrocyte sedimentation rate (ESR), white blood cell count with differential and platelet count. Biochemistry: Fasting glucose, blood urea nitrogen, creatinine, sodium, potassium, chloride, bicarbonate, calcium, phosphorous, total protein, albumin, total bilirubin, alkaline phosphatase, ALT, AST, CPK, hs CRP. Urinalysis (dipstick) to include: specific gravity, pH, glucose, ketones, blood, protein, nitrate, leukocyte esterase, urobilinogen and bilirubin. If any parameter on the dipstick is abnormal, a urine sample should be sent to the central laboratory for testing. If positive for proteins, microscopic analysis is performed by central laboratory.
- h* Serology testing includes hepatitis B surface antigen, hepatitis B surface antibody, hepatitis B core antibody, and hepatitis C antibodies.
- i* [REDACTED]
- j* Tuberculosis screen: history and QuantiFERON-TB Gold test. If result of QuantiFERON-TB Gold test is indeterminate, the test should be repeated.

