- k* In women of child-bearing potential. After Visit 4 (W4) between study visits the patient will have a urine pregnancy test at home on a monthly basis. Patients will be given sufficient urine pregnancy kits to take home at each successive visit for monthly testing up until the end of study visit. When the testing coincides with a study visit as indicated in the flow chart, the results should be reported in the e CRF. When the testing is done at home between study visits, the results should be collected by the Investigator during the monthly phone calls and reported in the e CRF. If any interim urine pregnancy test performed by the patient is positive, the patient should immediately report to the investigator for appropriate follow-up and pregnancy reporting as appropriate.
- l* Local tolerability of SC injections will be assessed by the study nurse either at patient's place or at the site level for the inter-visit SC injection once a week. A Patient booklet to record information on injections at home will be provided to the patient at baseline and will be reviewed at each visit by Investigator.
- m* The follow-up period with no study treatment is due for patients who discontinue permanently the study treatment OR patients who complete the study.
- n* PK samples during Visits 2-9 will be collected predose (within 2 hours before each dose administration) and PK samples during Visit 10 will be collected in the morning.
- o* ADA samples will be collected at approximately the same times as the PK samples.
- p* Additional optional sampling will be performed 5 to 10 days after last dose in a subgroup of at least 30 patients per arm.
- q* Pulmonary function tests include DLCO, FVC, FEV1, TLC and RV. FEV1, TLC and RV will only be done at screening and at baseline. DLCO will be measured locally at the investigational site; spirometry test will be done locally but measured by a central laboratory.
- r* Will be measured under ambient air for all patients. For patients under oxygenotherapy, pulse oximetry will be measured under oxygenotherapy and then, after 10 minutes breathing ambient air at rest.
- s* Will be performed at screening unless already done within 1 year prior to screening.
- t* At visits 6 to 10, if oxygen saturation is less than 88% under ambient air at rest, patient should perform 6-MWT under 4L oxygen
- u* EQ-5D-5L will be measured at Visit 2 (baseline visit), Visit 8 (W36) and Visit 9 (W 52).

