8 STUDY TREATMENTS

8.1 INVESTIGATIONAL MEDICINAL PRODUCT(S)

A complete description of the Investigational Medicinal Product (IMP) and its proper handling will be provided in a pharmacy manual.

- Pharmaceutical form
 - SAR156597 solution for injection at 100 mg/mL: SAR156597 is supplied as a sterile freeze-dried powder for solution for injection. Each vial is overfilled with 125 mg of SAR156597 freeze-dried powder, and the final solution for injection is obtained by reconstitution of the entire vial content with 1.1 mL of water for injection, leading to an amount of 125 mg of SAR156597 drug substance in a total volume of 1.25 mL, that is a 100 mg/mL of SAR156597 solution. 1 mL of this 100 mg/mL SAR156597 solution can then be withdrawn for dose administration. 2 drug product vials are thus needed to reach a 200 mg dose.
 - Placebo consists of liquid with the same excipients as those of the reconstituted SAR156597 formulation, filled at nominal volume of 1.5 mL. Two vials are necessary, 1 mL will be taken from each vial to prepare 2 mL syringe.
- Method of preparation

At the study site, reconstitution of the IMP must be done by personnel other than those administering the drug and making clinical observations (e.g. pharmacist) to maintain the treatment blind (Refer to [Section 8.4](#)).

- At patient's home, reconstitution must be done by healthcare professionals (e.g. visiting nurse) out of view of patients and their families/caregivers.
- The IMP should be reconstituted the day of dosing (no more than 3 hours prior to SC injection), at room temperature.
- Dose of drug per administration
 - SAR156597 qw arm: one injection of SAR156597 200 mg administered subcutaneously every week
 - SAR156597 q2w arm: one injection of SAR156597 200mg administered subcutaneously once every 2 weeks alternating with one injection of placebo administered subcutaneously once every 2 weeks
 - Placebo arm: one injection of placebo administered every week

- Route and method of administration

The route and method of administration are subcutaneous in the abdomen. Subcutaneous injection sites should be alternated between the 4 quadrants of the abdomen (avoiding navel and waist areas) so that the same site is not injected for two consecutive weeks. Exact site of each injection will be documented on source document.

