The IMP is administered every 7 days +/- 2 days from initial IMP administration. This is permitted per protocol to accommodate special circumstances, eg. laboratory results pending, ongoing AE, patient scheduling difficulty.

If IMP administration is missed or temporarily discontinued, the initial schedule of injections should be resumed. This does not apply to permanent treatment discontinuation.

On days when the patient has a study visit, the IMP will be administered by the Investigator or delegate after clinic procedures and blood collection.

For doses not administered at the study site, the IMP will be administered by qualified site personnel and /or healthcare professionals (e.g. visiting nurse service).

Patients should be monitored by site personnel/visiting nurse for at least 30 minutes after each administration for potential signs and symptoms that may suggest a hypersensitivity reaction.

[For Czech Republic only per local requirement: Patients should be monitored at the study site by site personnel for a minimum of 2 hours after the first administration of IMP and for a minimum of 1 hour after the next 5 administrations for potential signs and symptoms that may suggest a hypersensitivity reaction. For the subsequent IMP administrations, patients should be monitored by site personnel/visiting nurse for at least 30 minutes after each administration.]

For doses not given at study site, a booklet will be provided to the patient to record information related to the injections; this booklet will be completed by the visiting nurse after each injection and will be kept as source data in the patient's study file. Patients will be instructed to bring the booklet back at the subsequent site visit for Investigator's review.

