8.3 BLINDING PROCEDURES

8.3.1 Methods of blinding

SAR156597 and placebo will be provided in treatment kits indistinguishable in appearance and will be labeled with a treatment kit number. The randomized treatment kit number list will be generated by Sanofi.

In accordance with the double-blind design, study patients, Investigators, and study site personnel (except the personnel who conduct the reconstitution of the IMP and preparation of syringes for injection) will remain blinded to study treatment and will not have access to the randomization (randomized treatment kit number) except under circumstances described in [Section 8.3.2](#).

To maintain blinding, since unreconstituted placebo and SAR156597 vials are not matched for appearance, the personnel involved with dose preparation will be required to agree not to reveal to other study personnel the type of IMP solution (SAR156597 vs. placebo) in the vials/syringes.

For doses administered at patient's home, visiting nurses will be requested to reconstitute the IMP out of view of patients and their families/caregivers and to sign a confidential agreement for not disclosing the IMP box content.

Also to protect the blind, SAR156597 and placebo will be supplied in a 2 week treatment kit containing individually 2 Tamper Evident sealed treatment boxes (2 vials per box / 2 boxes per kit).

Each inner box will contain 2 vials and will be labeled as "Box 1" (week 1 treatment) and "Box 2" (week 2 treatment). Each weekly treatment box will be sealed with a tamper evident seal.

The outer kit, also tamper evident sealed will contain the 2 inner boxes and extra tamper seals.

After administration of week 1 treatment, the person preparing the dose will put the empty vials back in the original inner box 1, put the empty box 1 back in the outer kit and tamper evident sealed it until week 2 administration. After administration of week 2 treatment, the same procedure will be applied for box 2.

During monitoring visit, the unblinded monitor will break the tamper evident seal to perform IMP accountability. The monitor will tamper seal the outer box after performing IMP accountability.

The Investigator must not open the returned tamper sealed boxes.

Refer to [Section 10.5](#) for suspected unexpected serious adverse drug reaction unblinding by the Sponsor.

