**Figure 1 - Graphical study design (screening period, double-blind period and follow-up period)**

R\*: randomization  
Sc: subcutaneous  
D: day  
W: week

Approximately 300 patients will be randomized in a ratio 1:1:1 to the following three treatment arms:

- SAR156597 (qw) arm (n = 100): Patients will receive SAR156597 administered subcutaneously in 200 mg doses once every week (qw)
- SAR156597 (q2w) arm (n = 100): Patients will receive SAR156597 administered subcutaneously in 200 mg doses once every 2 weeks (q2w) alternating with placebo subcutaneously once every 2 weeks
- Placebo (qw) arm (n = 100): Patients will receive placebo subcutaneously once every week.

The study population will be stratified at baseline according to a background therapy with pirfenidone or nintedanib (standard of care for IPF in authorized countries).

The study will last up to 68 weeks as follows:

- Up to 4 weeks of screening
- 52 weeks of study treatment (from Day 1 dosing to Week 52 dosing)
- 12 weeks of follow-up

The total duration will be approximately 64 weeks (excluding screening period) per patient.

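### Up to 85% of scheduled injections may be prepared, given and locally assessed at home by one nurse who knows whether the dose is active or placebo, and the SAP pools these reactions without a split or caveat

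*Protocol*

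**What the plan says.** **At the site.** Protocol 8.1 (method of preparation) says "reconstitution of the IMP must be done by personnel other than those administering the drug and making clinical observations", and gives protection of the blind as the reason.

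**At home.** The same list says "reconstitution must be done by healthcare professionals (e.g. visiting nurse) out of view of patients and their families/caregivers". Protocol 8.3.1 repeats the concealment from patient and family and adds a signed confidentiality agreement. It acknowledges the reason for these measures: "since unreconstituted placebo and SAR156597 vials are not matched for appearance". According to 8.1, active is freeze-dried powder and placebo is a liquid.

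**Who gives and records the dose.** Flow chart footnote d reads: "Study treatment to be administered once a week, either at the site level or at home by a nurse". For doses away from the site, 8.1 allows site personnel or a visiting nurse to inject and to monitor the patient for 30 minutes. It then says "this booklet will be completed by the visiting nurse after each injection"; the booklet is kept as source data. Footnote l begins "Local tolerability of SC injections will be assessed by the study nurse either at" and goes on to name the patient's home or the site as the place.

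**Analysis.** For local injection-site reactions, SAP 2.4.5.1 tabulates incidence, highest intensity, symptom size, time to first reaction and events per injection. None of these is split by where the injection was given, and nothing is said about the assessor's knowledge of treatment.

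**The concern.** The protocol sets a safeguard for the site and has no equivalent for the home. Concealment and non-disclosure stop the nurse from telling others what is in the vial. They do not blind the nurse as an observer.

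Local tolerability is a listed safety endpoint with graded severity and pain (protocol summary). Severe injection-site reactions are an adverse event of special interest (10.4.1.3) and lead to permanent discontinuation (10.3.3). The Appendix E grades rest partly on judgement: pain, tenderness, itching and interference with activity. If the person who elicits and records these knows the product, the record can create or enlarge a difference between active and placebo. The pooled tables would not show that this had happened.

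**Working it through.** **1. Number of scheduled injections.** SAP 1.4 describes "52 weeks of study treatment (from Day 1 dosing to Week 52 dosing", and dosing is weekly. Weeks 0 to 52 inclusive give 52 + 1 = 53 injections for a completer.

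**2. Doses on study-visit days.** Protocol 8.1: "On days when the patient has a study visit, the IMP will be administered by the Investigator or delegate after clinic procedures and blood collection". The dosing visits V2 to V9 fall at Weeks 0, 2, 4, 6, 12, 24, 36 and 52, so there are 8.

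**3. Ceiling for home doses.** 53 − 8 = 45, and 45/53 = 84.9%.

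**4. Czech Republic.** The first six doses must be observed at the site, which adds Weeks 1, 3 and 5. That makes 8 + 3 = 11 site doses; 53 − 11 = 42, and 42/53 = 79.2%.

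**5. Range for the unknown home share.** Footnotes d and l allow doses between visits to be given at the site, and no document states how many were. Let *h* be the assumed fraction given at home. The share of all injections is then *h* × 45/53:

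| Assumed *h* | Share of all 53 injections |
|---|---|
| 100% | 84.9% |
| 90% | 76.4% |
| 75% | 63.7% |
| 50% | 42.5% |
| 25% | 21.2% |

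**6. Telephone contacts.** Nine calls also ask about the injection site: eight during treatment (10.1.6) and one at Week 58 (10.1.9). If each counts as an assessment, the ceiling is 45/(53 + 9) = 45/62 = 72.6%.

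**7. Who does what.**

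| Step | Study visit | Home |
|---|---|---|
| Prepares | Must not inject or observe | Healthcare professional, visiting nurse as the example |
| Injects | Investigator or delegate | Site personnel or visiting nurse |
| Records local tolerability | Blinded site staff | Visiting nurse, in the booklet |
| Second, blinded person | Required | Not provided for |

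**8. Can the study-visit doses serve as a blinded comparison?** All eight fall in even weeks. In the q2w arm active and placebo alternate weekly, and 8.1 says that a missed dose does not shift the schedule. The q2w study-visit doses are therefore all active or all placebo, depending on which comes first. In the qw and placebo arms every dose is the same product, so the restriction does not change the product mix there.

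**The case against.** **The 85% is a ceiling.** A reader might infer that about 85% of local-tolerability assessments are in fact unblinded. The documents do not support that. The figure assumes a completer and every between-visit dose at home.

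**One nurse in all roles is permitted but not stated.** Protocol 8.1 names a visiting nurse as an example of the preparer, allows site personnel to inject, and footnote l calls the assessor the study nurse. No passage says who assigns the Appendix E grade for a home dose. This limits the claim to what may happen. The plan still does not rule it out.

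**A blinded Investigator stands between booklet and analysis.** Protocol 10.4.3 has the Investigator record onset, intensity and causality, and the SAP tabulates adverse events and the e-CRF complementary form, not raw booklet grades. This stands and weakens the effect. It does not remove it, because the Investigator's review between visits draws on the nurse's record, and nine calls do not replace observation after each injection.

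**The symptoms are felt by a blinded patient, and redness and swelling have centimetre thresholds.** This is also true, but the nurse still elicits and enters them.

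**The SAP does not claim blinded assessment.** A reader might take its phrase about double-blind injections as such a claim. It labels the product. SAP 2.4.5 describes the safety analysis as essentially descriptive, though it allows relative risks versus placebo with 95% intervals.

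**Conclusion.** The point holds as a gap in design and reporting. Up to 45 of 53 scheduled injections (85%; Czech Republic up to 42 of 53, 79%) may be prepared, given and locally assessed by one person who knows the product, and the SAP neither separates nor flags these data. The figures rest on full completion and on all permitted doses being given at home. If half of the between-visit doses were given at home, the share would be 42.5%. The size of any bias in reaction rates cannot be derived from the documents.

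Two stronger conclusions do not follow. First, the primary endpoint is not directly affected: FVC is performed at site visits and measured by a central laboratory (protocol 9.1.4.1). Second, a reader might conclude that the study-visit injections should become the main comparison between arms. Step 8 shows why not: for q2w that set contains only one of the two alternating products, so it cannot represent the regimen.

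**What to change.** 1. **Booklet, for doses still to be given.** Have the patient rate pain, tenderness and itching before the nurse enters any grade. This needs no extra staff. It does change a source document across the 109 initiated sites that SAP 1.1 reports, and it cannot cover doses already given.
2. **SAP 2.4.5.1.** Beside the pooled table, add a descriptive tabulation of injection-site reactions (incidence, intensity, events per injection) by setting of the most recent injection: study-visit dose versus other. Use the study-visit set as a sensitivity check with blinded preparation for qw versus placebo only. Label the q2w column as reflecting a single alternating product.
3. **Study report.** State that local tolerability after home injections may have been assessed by an unblinded nurse.

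The cost is one extra table, a booklet instruction and a sentence in the report. The sensitivity set is small: 8 of 53 injections per completer (15.1%). Setting is also an imperfect stand-in for assessor blinding, because a reaction that emerges after a study-visit dose may first be seen by the home nurse a week later. If no further doses remain to be given, items 2 and 3 can still be done.

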8.2 NONINVESTIGATIONAL MEDICINAL PRODUCT(S)

Not applicable

8.3 BLINDING PROCEDURES

8.3.1 Methods of blinding

SAR156597 and placebo will be provided in treatment kits indistinguishable in appearance and will be labeled with a treatment kit number. The randomized treatment kit number list will be generated by Sanofi.

In accordance with the double-blind design, study patients, Investigators, and study site personnel (except the personnel who conduct the reconstitution of the IMP and preparation of syringes for injection) will remain blinded to study treatment and will not have access to the randomization (randomized treatment kit number) except under circumstances described in [Section 8.3.2](#).

To maintain blinding, since unreconstituted placebo and SAR156597 vials are not matched for appearance, the personnel involved with dose preparation will be required to agree not to reveal to other study personnel the type of IMP solution (SAR156597 vs. placebo) in the vials/syringes.

For doses administered at patient's home, visiting nurses will be requested to reconstitute the IMP out of view of patients and their families/caregivers and to sign a confidential agreement for not disclosing the IMP box content.

Also to protect the blind, SAR156597 and placebo will be supplied in a 2 week treatment kit containing individually 2 Tamper Evident sealed treatment boxes (2 vials per box / 2 boxes per kit).

Each inner box will contain 2 vials and will be labeled as "Box 1" (week 1 treatment) and "Box 2" (week 2 treatment). Each weekly treatment box will be sealed with a tamper evident seal.

The outer kit, also tamper evident sealed will contain the 2 inner boxes and extra tamper seals.

After administration of week 1 treatment, the person preparing the dose will put the empty vials back in the original inner box 1, put the empty box 1 back in the outer kit and tamper evident sealed it until week 2 administration. After administration of week 2 treatment, the same procedure will be applied for box 2.

During monitoring visit, the unblinded monitor will break the tamper evident seal to perform IMP accountability. The monitor will tamper seal the outer box after performing IMP accountability.

The Investigator must not open the returned tamper sealed boxes.

Refer to [Section 10.5](#) for suspected unexpected serious adverse drug reaction unblinding by the Sponsor.

8.3.2 Randomization code breaking during the study

In case of an adverse event (AE), the code should only be broken in circumstances when knowledge of the IMP is required for treating the patient. If possible, contact should be initiated with the monitoring team before breaking the code.

Code breaking can be performed at any time by using the proper module of the interactive voice response system (IVRS)/interactive web response system (IWRS) and/or by calling any other phone number provided by the Sponsor for that purpose. If the blind is broken, the Investigator should document the date, time of day, and reason for code breaking.

If the blind is broken by the Investigator, for the above stated purpose, the patient must be withdrawn from treatment.

